### **8.11.4 Survival Status**

#### **Cohort A**

Collection of survival status will not be required for Cohort A.

#### **Cohort B**

To ensure current and complete survival data is available at the time of database locks, updated survival status may be requested during the course of the study by the Sponsor. For example, updated survival status may be requested prior to but not limited to an interim and/or final analysis. Upon Sponsor notification, all participants who do not/will not have a scheduled study visit or study contact during the Sponsor defined time period will be contacted for their survival status (excluding participants that have a previously recorded death event in the collection tool).

## **9 STATISTICAL ANALYSIS PLAN**

### **9.1 Statistical Analysis Plan Summary**

This section outlines the statistical analysis strategies and procedures for the primary, secondary, and exploratory analyses of the study.

If, after the study has begun, changes are made to primary and/or secondary objectives, or the statistical methods related to those objectives, then the protocol will be amended (consistent with ICH Guideline E9). Post hoc exploratory analyses will be clearly identified in the Clinical Study Report (CSR).

Full details are in the Statistical Analysis Plan, Section 9.2 through Section 9.12.

Study Design Overview	Phase 1, relative bioavailability, cross-over study of pembrolizumab administered via IV infusion or SC injection in participants with advanced melanoma (Cohort A) and of IV pembrolizumab Q6W dosing (Cohort B).
Treatment Assignment	
In Cohort A, participants will be randomized to 1 of 6 treatment arms and will receive 1 IV infusion and 2 SC injections over the first 3 cycles, followed by IV infusion of pembrolizumab for up to 35 cycles.
 
In Cohort B, participants will receive IV infusion of pembrolizumab Q6W for up to 18 cycles.
 
Enrollment into Cohort A takes priority over Cohort B.

Analysis Populations	
Cohort A:
 
PK (Primary): Per-Protocol (PP)
 
Safety (Secondary): All-Participants-as-Treated (APaT)
 
Cohort B:
 
Efficacy (Primary): Full Analysis Set (FAS)
 
PK (Secondary): Per-Protocol (PP)
 
Safety (Secondary): All-Participants-as-Treated (APaT)

Primary Endpoint(s)	
Cohort A: Pharmacokinetic parameters of pembrolizumab, including area under the curve (AUC), maximum concentration (<math>C_{max}</math>), bioavailability (F), absorption rate (Ka), time of maximum concentration (<math>T_{max}</math>), clearance (CL), and central volume of distribution (Vc)
 
Cohort B: ORR per RECIST 1.1. by BICR

Secondary Endpoints	
Cohort A:
 
 
• Circulating antidrug antibody levels
 
• Adverse events (AEs)
 
• Discontinuing study treatment due to an AE
 
• Responses to the injection site signs and symptoms questionnaire
 
 
Cohort B:
 
 
• DOR per RECIST 1.1 by BICR
 
• PFS per RECIST 1.1 by BICR
 

	
 
• OS
 
• Adverse events (AEs)
 
• Pharmacokinetics: Pharmacokinetic parameters of pembrolizumab, including AUC, Cmax, and Cmin after administration of 400 mg Q6W pembrolizumab
 

Exploratory	Cohort B 
 
• Circulating antidrug antibody levels
 

Statistical Methods for Pharmacokinetic Analyses	Cohort A: The relative bioavailability of pembrolizumab via SC injection will be estimated using AUC comparing with that via IV infusion. The log-transformed AUC of pembrolizumab will be analyzed with a linear mixed effects model with fixed effects terms for treatment and cycle. Point estimates for Geometric Mean Ratio (GMR, SC CCI versus IV, SC CCI versus IV) and their 90% confidence intervals (CIs) will also be calculated.
Statistical Methods for Safety Analyses	Summary statistics will be provided for the safety endpoints as appropriate.
Statistical Methods for Efficacy Analyses	Cohort B: Estimation of ORR; Estimation of DOR, PFS and OS using the Kaplan-Meier method.
Interim Analyses	No interim analysis is planned. Two PK analyses will be conducted during the study. The first PK analysis will occur when at least 30 participants have completed the first 3 cycles of this study in Cohort A. The second PK analysis will occur after Cycle 5 in Cohort B.
Multiplicity	No multiplicity adjustment is planned for this Phase 1 research design.
Sample Size and Power	There is no hypothesis testing. For Cohort A, assuming the true GMR of AUC between SC injection and IV infusion is 1.0, with 30 completers the 90% CI of the GMR will be (0.90, 1.11). For Cohort B, assuming the observed ORR is what is expected with pembrolizumab 200 mg Q3W for 35 cycles (~35%), 100 subjects will assure a 95% CI for the true ORR of approximately (25%, 45%).
Abbreviations: BICR=blinded independent central review; DOR=duration of response; ORR=objective response rate; OS=overall survival; PFS=progression-free survival; RECIST 1.1=Response Evaluation Criteria in Solid Tumors 1.1	

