### **9.4.3 Efficacy Endpoints (Cohort B)**

#### **9.4.3.1 Primary**

##### **Objective Response Rate (ORR) per RECIST 1.1 assessed by BICR**

Objective Response is defined as a best overall response of CR or PR. The details of the ORR analysis plan can be found in Section 9.6.1.1.

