### **9.5.2 Safety Analysis Population (Cohorts A and B)**

The All-Participants-as-Treated (APaT) population will be used for the analysis of safety data in this study, including injection site signs and symptoms. The APaT population consists of all participants who received at least 1 dose of study treatment. In case of treatment administration errors, participants will be analyzed according to the treatment they actually received.

At least 1 laboratory or vital sign measurement obtained subsequent to at least 1 dose of study treatment is required for inclusion in the analysis of each specific parameter. To assess change from baseline, a baseline measurement is also required.

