### **9.5.3 Efficacy Analysis Population (Cohort B)**

The APaT population will serve as the primary population for the analysis of efficacy data in this study.

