#### 9.6.2.1 Objective Response Rate (ORR)

ORR will be calculated as the ratio of the number of participants reported to have achieved a confirmed CR or PR verified by BICR, divided by the number of participants included in APaT population. Participants in the APaT analysis population without ORR assessments will be counted as non-responders.

A 95% exact binomial CI (based on method Clopper and Pearson,1934) will be calculated for the true ORR.

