#### 9.6.2.4 Duration of Response (DOR)

DOR will be summarized descriptively using the non-parametric Kaplan-Meier method. Only the subset of participants who show a CR or PR will be included in this analysis. Censoring rules for DOR are summarized in [Table 11](#).

Table 11 Censoring Rules for Duration of Response

Situation	Date of Progression or Censoring	Outcome
No progression nor death, no new anticancer therapy initiated	Last adequate disease assessment	Censor (non-event)
No progression nor death, new anticancer therapy initiated	Last adequate disease assessment before new anti-cancer therapy initiated	Censor (non-event)
Death or progression immediately after $\geq 2$ consecutive missed disease assessments or after new anti-cancer therapy, if any	Earlier date of last adequate disease assessment prior to $\geq 2$ missed adequate disease assessments and new anti-cancer therapy, if any	Censor (non-event)
Death or progression after $\leq 1$ missed disease assessments and before new anti-cancer therapy, if any	Progressive disease or death	End of response (Event)
Note: A missed disease assessment includes any assessment that is not obtained or is considered inadequate for evaluation of response. DOR = duration of response		

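### Does the Cohort B response rate have two denominators and two numerators?

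*Combined protocol and SAP*

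**What the plan says.** **Denominator.** The Analysis Populations row of Section 9.1 lists, for Cohort B, "Efficacy (Primary): Full Analysis Set (FAS"), and gives APaT on a separate line for safety. Section 9.5.3 states: "The APaT population will serve as the primary population for the analysis of efficacy data in this study". Section 9.5.2 defines the set: "The APaT population consists of all participants who received at least 1 dose of study treatment". Section 9.6.2.1 computes ORR from participants who "achieved a confirmed CR or PR verified by BICR, divided by the number of participants included in APaT population", and counts APaT participants without a response assessment as non-responders. Table 12 gives the same population and the same rule. Apart from the Section 9.1 entry, FAS appears only in the abbreviation list in Appendix 9.

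**Numerator.** Section 9.4.3.1 reads: "Objective Response is defined as a best overall response of CR or PR". The endpoint tables in the synopsis and in Section 3 require a confirmed CR or PR, as does Section 9.6.2.1. Section 8.2.1.2 sets the confirmatory scan at least 4 weeks after the first sign of response.

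**Duration of response (DOR).** Section 9.6.2.4 says: "Only the subset of participants who show a CR or PR will be included in this analysis". It does not mention confirmation. Table 12 excludes non-responders from DOR.

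**Which text carries the detail.** Section 9.1 says of itself: "Full details are in the Statistical Analysis Plan, Section 9.2 through Section 9.12".

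**The concern.** Cohort B is a single-arm, open-label group, and ORR with its confidence interval is its only primary efficacy result. Section 9.9 expects that result to resemble the roughly 35% seen with 200 mg every 3 weeks. With no comparator arm, a change of analysis set or of response definition goes straight into the estimate and does not cancel out.

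Section 9.1 lists FAS and APaT side by side, which suggests two different sets. A full analysis set often leaves out participants with no post-baseline assessment. Those participants can only be non-responders, so leaving them out would raise the rate. If 9.4.3.1 were read as admitting single-scan responses, the rate would rise again, and the responders analysed for DOR might differ from those counted in ORR. The worry is that the more favourable combination could be picked once the data are known.

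**Working it through.** **1. Reproduce the plan's figure.** Section 9.9 assumes 35 responders among 100 participants and the Clopper-Pearson method. With x = 35 and n = 100:

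- lower limit = Beta quantile(0.025; x, n − x + 1) = Beta quantile(0.025; 35, 66) = 25.73%
- upper limit = Beta quantile(0.975; x + 1, n − x) = Beta quantile(0.975; 36, 65) = 45.18%

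This matches the stated (25.7%, 45.2%). The approximate (25%, 45%) in Section 9.1 is a looser rounding of the same interval.

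**2. Compare the texts on the denominator.**

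| Place | Population | Participants without assessment |
|---|---|---|
| 9.1 (summary) | FAS, undefined | not stated |
| 9.5.3 | APaT | not stated |
| 9.6.2.1 | APaT | non-responders |
| Table 12 | APaT | non-responders, kept in the denominator |

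Three detailed places agree. The one that differs is a summary that defers to them and names a set with no membership rule, so it could not be programmed as it stands.

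**3. Compare the texts on the numerator.**

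| Place | Confirmation |
|---|---|
| Synopsis and Section 3 endpoint tables | required |
| 9.6.2.1 | required |
| 8.2.1.2 | scan scheduled at least 4 weeks later |
| 9.4.3.1 | not mentioned |

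Section 9.4.3.1 does not say that unconfirmed responses count. It refers to the ORR analysis section for details, but by the number 9.6.1.1, which does not exist. Section 9.4.3 misnumbers the DOR and PFS pointers in the same way (9.6.1.4 and 9.6.1.2). In each case the last digit fits the real section: 9.6.2.1, 9.6.2.4 and 9.6.2.2.

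**4. Size of the shift if the detailed sections were ignored.** The documents give no rate of missing assessments, of undosed participants or of unconfirmed responses, so every count below is an assumption.

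| Assumed reading | Calculation | ORR (exact 95% CI) | Shift, points |
|---|---|---|---|
| Detailed sections | 35/100 | 35.0% (25.7, 45.2) | 0 |
| FAS drops 2 dosed, unassessed | 35/98 | 35.7% (26.3, 46.0) | +0.7 |
| FAS drops 5 | 35/95 | 36.8% (27.2, 47.4) | +1.8 |
| FAS drops 10 | 35/90 | 38.9% (28.8, 49.7) | +3.9 |
| 3 unconfirmed responses added | 38/100 | 38.0% (28.5, 48.3) | +3.0 |
| 5 unconfirmed responses added | 40/100 | 40.0% (30.3, 50.3) | +5.0 |
| 5 dropped and 5 added | 40/95 | 42.1% (32.0, 52.7) | +7.1 |

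The direction is not fixed either. If FAS meant all allocated participants, with 1 to 3 never dosed in addition to 100 dosed, ORR would fall to 35/101 = 34.7% or 35/103 = 34.0%. That is a shift of −0.3 to −1.0 point.

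The rows that drop dosed participants conflict with the non-responder rule in 9.6.2.1 and Table 12. The rows that add unconfirmed responses conflict with the confirmation requirement in 9.6.2.1 and the endpoint tables.

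**The case for a change.** The best argument for acting is that a primary endpoint should not be tied anywhere to an undefined population. Section 9.1 uses both labels in one cell, so FAS is hard to read as another name for APaT. The pointer that would complete 9.4.3.1 leads nowhere, and none of the DOR descriptions says confirmed. Correcting all this costs only wording.

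The textual facts stand: the label is wrong, a word is missing and the section numbers are off. The inference that two defensible analyses exist does not stand. Choosing a set that drops unassessed participants would contradict 9.5.3, 9.6.2.1 and Table 12 together. Section 9.1 also requires a protocol amendment if the methods for primary objectives change after the study has begun, and requires post hoc exploratory analyses to be identified as such. Response is read by blinded central review, which limits the influence of open-label knowledge on the numerator.

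On DOR the text is silent and sets up no rival definition. Table 12 fixes the non-responder rule for ORR and excludes non-responders from DOR in the same table, so the natural reading is a single responder set.

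**Conclusion.** The concern does not call for a change to the plan. The FAS entry is a label in a summary that conflicts with three consistent detailed sections to which the summary defers. The missing word in 9.4.3.1 and in the DOR text is a gap that an analyst would fill from 9.6.2.1 and the endpoint tables.

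Followed as written, the plan yields confirmed CR or PR by central review over all dosed participants. The planning value stays at 35.0% (25.7% to 45.2%), a shift of zero. Larger shifts need both assumed counts and a breach of the detailed text. Section 9.3 states that no hypothesis is tested, and the plan sets no threshold for ORR, so no decision rule hangs on the difference. The conclusion rests on reading Section 9.1 as subordinate to Sections 9.2 to 9.12, which is what it says about itself. Tidying the label, the word and the section numbers would help readers but would alter no result.

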## 9.2 Responsibility for Analyses/In-house Blinding

The statistical analyses of the data obtained from this study will be the responsibility of the Clinical Biostatistics department of the Sponsor.

The study is open-label; participants, investigators, and Sponsor personnel will be aware of participant treatment assignment after each participant is enrolled and treatment is assigned. Allocation to treatment in Cohort A will be randomized. There will be direct treatment assignment for Cohort B.

## 9.3 Hypotheses/Estimation

Objectives of the study are outlined in Section 3.0. No hypotheses are being tested in this study.

## 9.4 Analysis Endpoints

### 9.4.1 Pharmacokinetics Endpoints (Cohorts A and B)

Pharmacokinetic endpoints are PK parameters of pembrolizumab after IV (200 mg Q3W) and SC administration including area under the curve (AUC), maximum concentration ( $C_{max}$ ), bioavailability (F), absorption rate (Ka), time of maximum concentration ( $T_{max}$ ), clearance (CL), and central volume of distribution (Vc). PK endpoints also include AUC,  $C_{max}$ , and  $C_{min}$  after IV infusion 400 mg Q6W.

In addition, the development of circulating anti-pembrolizumab antibodies (if applicable) will be evaluated following IV 200 mg Q3W and SC administration, as well as IV 400 mg Q6W pembrolizumab administration.

### 9.4.2 Safety Endpoints (Cohorts A and B)

Safety and tolerability will be assessed by clinical review of all relevant parameters including AEs, laboratory tests, and vital signs, as well as the injection site signs and symptoms questionnaire.

A description of safety measures is provided in Section 8.3 and Section 8.4.

### **9.4.3 Efficacy Endpoints (Cohort B)**

#### **9.4.3.1 Primary**

##### **Objective Response Rate (ORR) per RECIST 1.1 assessed by BICR**

Objective Response is defined as a best overall response of CR or PR. The details of the ORR analysis plan can be found in Section 9.6.1.1.

#### **9.4.3.2 Secondary**

##### **Duration of Response (DOR) per RECIST 1.1 assessed by BICR**

For participants who demonstrate CR or PR, DOR is defined as the time from first documented evidence of CR or PR until disease progression or death due to any cause, whichever occurs first. See Section 9.6.1.4 for definition of censoring.

##### **Progression-free Survival (PFS) per RECIST 1.1 assessed by BICR**

PFS is defined as the time from the first day of study treatment to the first documented disease progression or death due to any cause, whichever occurs first. See Section 9.6.1.2 for definition of censoring.

##### **Overall Survival (OS)**

OS is defined as the time from the first day of study treatment to death due to any cause. Participants without documented death at the time of the final analysis will be censored at the date of the last follow-up.

### **9.5 Analysis Populations**

#### **9.5.1 Pharmacokinetic Analysis Population (Cohorts A and B)**

The Per-Protocol (PP) population will be used for the analysis of PK data in this study. The PP population consists of the subset of participants who complied with the protocol sufficiently to ensure that their data will be likely to exhibit the effects of treatment, according to the underlying scientific model. Compliance includes such considerations as exposure to treatment, availability of measurements, and the absence of major protocol violations. Any participants or data values excluded from the analyses will be identified, along with the reasons for exclusion, in the CSR. At the end of the study, all participants who were compliant with the study procedures and have available data from at least 1 treatment will be included in the PP analysis dataset.

### **9.5.2 Safety Analysis Population (Cohorts A and B)**

The All-Participants-as-Treated (APaT) population will be used for the analysis of safety data in this study, including injection site signs and symptoms. The APaT population consists of all participants who received at least 1 dose of study treatment. In case of treatment administration errors, participants will be analyzed according to the treatment they actually received.

At least 1 laboratory or vital sign measurement obtained subsequent to at least 1 dose of study treatment is required for inclusion in the analysis of each specific parameter. To assess change from baseline, a baseline measurement is also required.

### **9.5.3 Efficacy Analysis Population (Cohort B)**

The APaT population will serve as the primary population for the analysis of efficacy data in this study.

## **9.6 Statistical Methods**

### **9.6.1 Statistical Methods for Pharmacokinetic and Antidrug Antibodies Data (Cohorts A and B)**

#### **Cohort A**

Primary/final PK analysis will be conducted when at least 30 participants have completed the first 3 cycles of this study. Along with the safety data, the PK analysis will be used for programmatic decision making purposes. The study will not be discontinued regardless of the outcome of the PK analysis.

The relative bioavailability of pembrolizumab via SC injection will be estimated using AUC comparing with that via IV infusion. The log-transformed AUC of pembrolizumab will be analyzed with a linear mixed effects model with fixed effects terms for treatment and cycle. An unstructured covariance matrix will be used to allow for unequal treatment variances and to model the correlation between different treatment measurements within the same subject via the REPEATED statement in SAS PROC MIXED. Kenward and Roger's method will be used to calculate the denominator degrees of freedom for the fixed effects (DDFM=KR). If the model fails to converge, a simpler covariances structure, such as heterogeneous-compound symmetry, will be used.

If the concentration of pembrolizumab observed in the pre-dose sample of Treatment Cycle 2 or Cycle 3 is <5% of the  $C_{max}$  observed in the same cycle, this level of carry-over can be considered negligible and no correction is needed. However, if the concentration observed in the pre-dose samples is  $\geq 5\%$  of the  $C_{max}$  observed in the same cycle, all concentrations in that cycle will be adjusted (assuming linear PK) for the impact of the carry-over as specified by the equation below. If carry-over adjustment is necessary in any given cycle, the adjustment will be made for all subjects with quantifiable predose concentrations before

non-compartmental PK analysis for AUC and statistical model fitting. In addition, a reduced model may be explored to fit the Treatment Cycle 1 data only. In this model treatment will be included as a factor. The key covariates will also be considered.

$$C_{adj} = C_{orig} - CPD * e^{-(K_e)(t)}$$

Where:

$C_{adj}$  = carry-over-adjusted concentration

$C_{orig}$  = observed concentration

CPD = original predose concentration

$K_e$  = slope of terminal phase (elimination constant  $\lambda_z$  in Phoenix) of the previous cycle

t = time of  $C_{orig}$  compared to predose

Back-transformed Geometric Mean of AUC as well as its 95% CI will be calculated by treatment. Point estimates for Geometric Mean Ratio (GMR, SC [REDACTED] versus IV, SC [REDACTED] versus IV) and their 90% confidence intervals (CIs) will also be calculated. Other PK parameters including  $K_a$ ,  $C_{max}$ , CL, and  $V_c$  will be analyzed in a similar fashion.

Antidrug antibodies data will be summarized by treatment and visit. Relationship between the presence/absence of positivity for ADA and PK of pembrolizumab will be explored.

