## **3 HYPOTHESIS, OBJECTIVES, AND ENDPOINTS**

Male/female participants of at least 18 years of age with advanced melanoma will be enrolled in this study.

Objectives	Endpoints
Primary	
Cohort A 
 
To characterize the pharmacokinetic (PK) profile, including the absorption phase, of pembrolizumab following subcutaneous (SC) injection [CCI] [redacted]
 
To estimate the relative bioavailability of pembrolizumab via SC injection [CCI] [redacted] versus intravenous (IV) infusion (200 mg; 25 mg/mL)
 
	
 
Pharmacokinetic parameters of pembrolizumab, including area under the curve (AUC), maximum concentration (<math>C_{max}</math>), bioavailability (F), absorption rate (<math>K_a</math>), time of maximum concentration (<math>T_{max}</math>), clearance (CL), and central volume of distribution (<math>V_c</math>)
 

Primary	
Cohort B 
 
To evaluate objective response rate (ORR) per RECIST 1.1 as assessed by blinded independent central review (BICR)
 
	
 
Participants who have a confirmed CR or PR
 

Secondary	
Cohort A 
 
To evaluate the development of circulating anti-pembrolizumab antibodies (if applicable), following SC pembrolizumab
 
	
 
Antidrug antibody levels
 

 
To determine the safety and tolerability of SC pembrolizumab during the first 3 treatment cycles based on the proportion of adverse events (AEs)
 
	
 
Adverse events (AEs)
 
Study drug discontinuations due to AEs
 

 
To monitor the safety and tolerability of IV pembrolizumab during the first 3 treatment cycles and after Cycle 3 based on the proportion of AEs
 
	
 
Adverse events (AEs)
 
Study drug discontinuations due to AEs
 

Objectives	Endpoints

 
To determine the tolerability of SC pembrolizumab at the injection site during the first 3 treatment cycles based on the proportion of injection site signs and symptoms
 
	
 
Responses to an injection site signs and symptoms questionnaire
 

Secondary	
Cohort B	

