#### **4.2.1.2 Pharmacokinetic Endpoints**

##### **Cohort A**

A primary objective of this trial is to characterize the PK profile and relative bioavailability of pembrolizumab following administration as a SC injection versus an IV infusion. The serum concentrations of these agents will serve as the primary readout for the PK, and these data will be used to derive PK parameters. Furthermore, the results of these analyses will be

used in conjunction with the safety and exploratory endpoint data to help assess future dosing strategies for administering pembrolizumab SC.

To evaluate pembrolizumab immunogenicity and pembrolizumab exposure after SC administration, sample collections for analysis of antidrug antibodies (ADA) and PK are currently planned as shown in the SoA (Section 1.3). Blood samples will be obtained to measure PK of serum pembrolizumab. The pembrolizumab serum concentrations at planned visits and times will be summarized.

Pharmacokinetic data will also be analyzed using nonlinear mixed effects modeling. Based on PK data obtained in this study as well as PK data obtained from previous studies, an integrated population PK analysis will be performed to characterize PK parameters (absorption rate [Ka], bioavailability [F], clearance [CL], central volume of distribution [Vc]) of pembrolizumab following SC and IV administration.

Pharmacokinetic endpoints in this study include:

- Pharmacokinetic parameters of pembrolizumab , including area under the curve (AUC), maximum concentration ( $C_{max}$ ), bioavailability (F), absorption rate (Ka), time of maximum concentration ( $T_{max}$ ), clearance (CL), and central volume of distribution (Vc).

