### 4.3 Justification for Dose

The primary purpose of Cohort A in this study is to establish the SC dose and volume for further clinical development. Two SC solutions have been manufactured [REDACTED] and will be used in Cycles 1 to 3 of this study, corresponding to a dose of [REDACTED] that assumes 70% bioavailability for the SC formulation relative to IV (dose = 200 mg infusion given over 30 minutes in Cycles 1 to 3) [Zhao, L., et al 2013].

The planned dose of pembrolizumab for Cycle 4 onwards in this study is 200 mg IV infusion Q3W. Based on the totality of data generated in the Keytruda development program, 200 mg Q3W is the appropriate dose of pembrolizumab for adults across all indications and regardless of tumor type. As outlined below, this dose is justified by:

- Clinical data from 8 randomized studies demonstrating flat dose- and exposure-efficacy relationships from 2 mg/kg Q3W to 10 mg/kg every 2 weeks (Q2W),
- Clinical data showing meaningful improvement in benefit-risk including overall survival at 200 mg Q3W across multiple indications, and
- Pharmacology data showing full target saturation in both systemic circulation (inferred from pharmacokinetic [PK] data) and tumor (inferred from physiologically-based PK [PBPK] analysis) at 200 mg Q3W

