## Cohorts A and B

Individual values will be listed for each PK parameter by treatment, and the following (nonmodel-based) descriptive statistics will be provided: N (number of subjects with nonmissing data), arithmetic mean, standard deviation, arithmetic percent coefficient of variation (CV) (calculated as  $100 \times \text{standard deviation}/\text{arithmetic mean}$ ), median, minimum, maximum, geometric mean, and geometric percent CV (calculated as  $100 \times \sqrt{\exp(s^2) - 1}$ ), where  $s^2$  is the observed variance on the natural log-scale).

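### Does extending the AUC analysis to Ka, CL and Vc commit Cohort A to SC/IV ratios that cannot be estimated or carry no information?

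*Combined protocol and SAP*

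**What the plan says.** Section 9.6.1 (Cohort A) states that log AUC "will be analyzed with a linear mixed effects model with fixed effects terms for treatment and cycle". The outputs are a back-transformed geometric mean with 95% CI for each treatment, and geometric mean ratios with 90% CIs. The only ratios named are each SC treatment against IV. If the unstructured covariance cannot be fitted, the fallback is: "If the model fails to converge, a simpler covariances structure, such as heterogeneous-compound symmetry, will be used". One sentence then carries the approach to Ka, Cmax, CL and Vc, which "will be analyzed in a similar fashion". No parameter is excepted.

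Other places bear on how to read that sentence:

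- Section 3 lists Ka, CL and Vc among the Cohort A primary PK parameters. The first primary objective is to characterize the profile, "including the absorption phase, of pembrolizumab following subcutaneous (SC) injection".
- Section 4.2.1.2 names the source of Ka, F, CL and Vc: "an integrated population PK analysis will be performed to characterize PK parameters". Section 9.6.1 mentions non-compartmental analysis for AUC only.
- The part of Section 9.6.1 covering both cohorts adds descriptive output: "Individual values will be listed for each PK parameter by treatment", with geometric mean and geometric CV among the statistics.
- Section 4.3 says that the purpose of Cohort A "is to establish the SC dose and volume for further clinical development", and that the SC dose "assumes 70% bioavailability for the SC formulation relative to IV".

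**The concern.** Since the only ratios named for AUC are SC against IV, the obvious reading of the extending sentence is SC against IV for every parameter listed. That suits Cmax but not the other three.

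- **Ka.** There is no Ka after an infusion, so neither the IV geometric mean nor either SC/IV ratio exists. The covariance fallback does not help, because a treatment level is missing from the data; this is not a convergence problem.
- **CL and Vc.** In a population model where F carries the route difference and each participant has one CL and one Vc, the SC/IV ratio is 1 by construction. If apparent values (CL/F, V/F) were used instead, the ratio would mostly restate the AUC result and could be mistaken for a real difference in clearance or volume.

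The ratio that can be estimated for Ka, one SC concentration against the other, is not named, although it is relevant to choosing an SC volume. At stake is whether some listed primary PK parameters lack a usable analysis.

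**Working it through.** **Inputs.** Table 5: six arms of 5 participants, each receiving A and B (SC) and C (IV) once over Cycles 1 to 3. Section 9.9: within-subject SD of log AUC 0.25, 30 completers, true ratio 1.0. Section 4.3: assumed F of 0.70. The documents give no SD for Ka; the values used for it below are assumptions.

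**1. The plan's own figure.** The SE of a log ratio is √2 × 0.25/√30 = 0.0645. With t on 58 df, exp(±1.672 × 0.0645) gives (0.898, 1.114), matching the stated (0.90, 1.11). The AUC analysis is sound.

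**2. Estimability.**

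| | AUC | Ka |
|---|---|---|
| Profiles, 30 completers | 30 × 3 = 90 | 30 × 2 = 60 |
| Rank of the fixed-effects design | 1 + 2 + 2 = 5 | 1 + 1 + 2 = 4 |
| A vs C, B vs C | estimable | not estimable |
| A vs B | estimable | estimable |

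More participants would not alter this: with 36 there would be 36 × 2 = 72 SC profiles and still no IV value of Ka.

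**3. What Ka can give.** Table 5 puts A and B in each cycle for 10 participants, so A vs B is balanced over cycle. With 30 − 3 = 27 df and t = 1.703, the expected 90% CI around a ratio of 1 is exp(±1.703 × SD × √(2/30)):

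- SD 0.25: (0.90, 1.12)
- SD 0.60: (0.77, 1.30)

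These intervals show the precision of an optional extra comparison; they do not measure an error.

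**4. CL and Vc.**

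- Population model, F estimated separately, one CL and one Vc per participant: ratio = 1 exactly. The documents do not say whether there is one value per participant.
- Apparent clearance: CL/F = dose/AUC, so the SC/IV ratio of CL/F = dose ratio ÷ AUC ratio = 1/F. This gives 1/0.70 = 1.43, and 1.67 to 1.25 for F from 0.60 to 0.80. In one simulated 30-participant cross-over (dose ratio assumed 1/0.70), the log effects of A vs IV on AUC and CL/F were 0.0637 and 0.2930. They sum to 0.3567 = ln(1/0.70) and share an SE of 0.0613, so the CL/F ratio adds nothing to the AUC ratio.

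**5. Which case applies.** Section 4.2.1.2 treats F as a parameter distinct from CL and Vc and assigns all of them, with Ka, to the population analysis. Ka and central volume are compartmental-model quantities that a non-compartmental analysis does not return. The 1/F figures therefore describe an analysis the plan does not specify.

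**The case for a change.** The strongest argument for amending the text is that Ka, CL and Vc are listed primary PK parameters, that the extending sentence makes no exception, and that Section 9.1 requires an amendment when methods tied to primary objectives change. On that view the method should be written down, not worked out at analysis. Cohort A also tests two SC concentrations to settle dose and volume, so an SC-to-SC ratio of Ka with a CI would be useful, and the descriptive summaries supply neither.

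Part of this stands. The sentence is careless about Ka, and a clause limiting SC/IV ratios to parameters where they are defined would be tidier. The rest does not amount to a needed change:

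- Similar does not mean identical. Log-scale geometric means with CIs for the treatments that have a Ka satisfy the sentence. Leaving out a ratio that does not exist applies the stated method where it is defined; it does not change the method.
- No Cohort A objective in Section 3 asks for a formal comparison of the two SC treatments. Those objectives are to characterize the SC profile and to estimate bioavailability against IV. A Ka ratio is a reasonable extra, not a missing requirement.
- Tmax and Cmax also describe absorption and are in the same list, so Ka is not the only evidence on that phase.
- Section 9.3 says that no hypothesis is tested, and no decision rule uses a ratio of Ka, CL or Vc.

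**Conclusion.** This is missing detail that analysts will fill sensibly, and no change to the plan follows. The concern is right that two of the two SC/IV contrasts for Ka are non-estimable, and that an SC/IV ratio of CL or Vc would tell the reader nothing useful. The consequence is nil: software returns no estimate for the Ka contrast, the natural response is to report Ka for the two SC treatments, and the planned descriptive tables already do so. Relative bioavailability from AUC, the population estimate of F, Cmax, Tmax, the expected 90% CI of (0.90, 1.11) and the sample size are all unaffected.

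The conclusion rests on three points: Ka, CL and Vc come from the population PK analysis, as Section 4.2.1.2 says; the loose wording is read as allowing the method to be applied where it is defined; and no decision depends on the ratios in question. If SC clearance were nevertheless computed as dose/AUC, labelling it CL/F would be ordinary practice and would prevent the 1.43 from being misread.
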